## 8.10 Subgroup Analyses and Effect of Baseline Factors

To determine whether the treatment effect is consistent across various subgroups, the estimate of the between-group treatment effect (with a nominal 95% CI) for the primary endpoint will be estimated and plotted within each category of the following classification variables:

- Age category (<65 vs. ≥65 years)
- Sex (female vs. male)
- Race (white vs. non-white)
- Disease stage (III vs. IVM1a vs. IVM1b vs. IVM1c)
- ECOG status (0 vs. 1)
- BRAF mutation status (wild type vs. mutant with prior BRAF directed therapy vs. mutant with no prior BRAF directed therapy)
- PD-L1 status (positive vs. negative [includes indeterminate])
- LDH ( $\leq$  ULN vs.  $>$  ULN but  $<$  2X ULN vs.  $\geq$  2X ULN)

In addition, a Forest plot will be produced, which provides the estimated point estimates and confidence intervals for the treatment effect across the categories of subgroups listed above.

The consistency of the treatment effect will be assessed descriptively via summary statistics by category for the classification variables listed above.

## 8.11 Compliance (Medication Adherence)

**Pembrolizumab:** Drug accountability data for pembrolizumab will be collected during the study. Compliance with protocol-directed pembrolizumab will be measured by subjects: (1) receiving unscheduled study agent infusions/injections, (2) missing an infusion/injection, (3) receiving incorrect study agent dose, and (4) receiving an infusion at rate greater than 10 mL/min. Numbers and percentages of subjects and infusion/injection visits with any deviation in these measures will be reported for the ITT population.

**Epacadostat:** In this study, as part of the routine recording of the amount of study treatment taken by each subject will be counted, reviewed, and recorded at regular intervals. These results will be used to calculate subject compliance.

- For a subject who is followed for the entire study period, the “Number of Epacadostat Doses Should be on Therapy” is the total number of protocol specified doses from first treatment day to the last scheduled day for treatment administration for that subject. For a subject who discontinued from the study permanently, the “Number of Epacadostat Doses Should be on Therapy” is the total number of doses from first treatment day to the date the subject discontinued from the study.

Percent compliance is defined as “the number of doses the patient received on therapy” divided by “the number of doses the patient should have received on therapy” multiplied by 100.

Summary statistics will be provided on percent compliance by treatment group for the ITT population.

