Based on the Phase 1 safety data of epacadostat doses ranging from 25 mg BID up to 300 mg BID, a dose of 100 mg BID was selected for the Phase 2 portion of Study 202 and for this Phase 3 study of epacadostat to be combined with pembrolizumab 200 mg IV Q3W.

ORR in 19 evaluable subjects with treatment-naïve metastatic melanoma was 58% (11/19) with disease control rate of 74% (14/19). Median PFS has not been reached and all responses are ongoing with min follow up of 31.7 weeks.

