##### **5.8.1 Discontinuation of Treatment**

Discontinuation of treatment does not represent withdrawal from the trial.

As certain data on clinical events beyond treatment discontinuation may be important to the study, they must be collected through the subject's last scheduled follow-up, even if the subject has discontinued treatment. Therefore, all subjects who discontinue trial treatment prior to completion of the treatment period will still continue to participate in the trial as specified in Section 6.0 - Trial Flow Chart and Section 7.1.8.5 – Post-Trial.

Subjects may discontinue treatment at any time for any reason or be dropped from treatment at the discretion of the investigator should any untoward effect occur. In addition, a subject may be discontinued from treatment by the investigator or MSD if treatment is inappropriate, the trial plan is violated, or for administrative and/or other safety reasons. Specific details regarding procedures to be performed at treatment discontinuation are provided in Section 7.1.7 – Other Procedures.

A subject must be discontinued from treatment but continue to be monitored in the trial for any of the following reasons:

- The subject or subject's legally acceptable representative requests to discontinue treatment.
- The subject has a medical condition or personal circumstance which, in the opinion of the investigator and/or MSD, placed the subject at unnecessary risk from continued administration of study drug/vaccine.
- The subject has a confirmed positive serum pregnancy test.
- Confirmed radiographic disease progression outlined in Section 7.1.5 (exception if MSD approves treatment continuation).
- Unacceptable adverse experiences as described in Section 7.2.

- Any progression or recurrence of any malignancy, or any occurrence of another malignancy that requires active treatment. Note: **For France only**, a subject experiencing this condition must be discontinued from the trial.
- Intercurrent illness other than another malignancy as noted above that prevents further administration of treatment.
- Recurrent Grade 2 pneumonitis.
- Any toxicity listed in Section 5.2.1.2, [Table 2](#), with a requirement to permanently discontinue.
- Non-compliance with trial treatment or procedure requirements.
- Investigator's decision to discontinue treatment.
- Administrative reasons.
- Completed 35 treatments with pembrolizumab.

Note: 35 cycles (approximately. 2 years) are calculated from the first dose.

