- Discontinuation of treatment may be considered for subjects who have attained a confirmed CR and have been treated for at least 8 cycles (at least 24 weeks) and had at least 2 cycles of the combination (at least 2 doses of pembrolizumab) beyond the date when the initial CR was declared.

The End of Treatment and Follow-up visit procedures are listed in Sections 7.1.8.4 and the Trial Flow Chart - Section 6.0.

For subjects who are discontinued from treatment but continue to be monitored in the trial, see Section 6.0 – Trial Flow Chart, and Section 7.1.8.4 – Post-Trial for those procedures to be completed at each specified visit.

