## 5.8.2 Withdrawal from the Trial

A subject must be withdrawn from the trial if the subject or subject's legally acceptable representative withdraws consent from the trial.

**For France only:** A subject must be discontinued from the trial for the following reason:

- Any progression or recurrence of another malignancy, or any occurrence of another malignancy that requires active treatment.

If a subject withdraws from the trial, they will no longer receive treatment or be followed at scheduled protocol visits.

Specific details regarding procedures to be performed at the time of withdrawal from the trial including the procedures to be performed should a subject repeatedly fail to return for scheduled visits and/or if the study site is unable to contact the subject, [REDACTED]

[REDACTED] are outlined in Section 7.1.7  
– Other Procedures.

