##### **7.1.8.4.2 Follow-Up Visits**

**NOTE: As of Amendment 10, this section is no longer applicable. A subject will be considered to have completed this study once they have attended the Safety Follow-up Visit. Subjects currently in follow-up are considered to have completed the study; these subjects are not required to attend any further visits. Assessment and recording of AEs will be performed as per Section 7.2.**

Subjects who discontinue study treatment for a reason other than disease progression will move into the Follow-Up Phase and should be assessed every 9 weeks ( $63 \pm 7$  days) from Week 12 up to Week 102 by radiologic imaging to monitor disease status then every 12 weeks ( $84 \text{ days} \pm 7 \text{ days}$ ) thereafter. Every effort should be made to collect information regarding disease status until the start of new anti-cancer therapy, disease progression, death, and end of the study, or if the subject begins retreatment as detailed in Section 7.1.8.3. Information regarding poststudy antineoplastic treatment will be collected if new treatment is initiated.

Subjects who are eligible to receive retreatment according to the criteria in Section 5.2.2 will move from the Follow-Up Phase to the Second Course Phase (Retreatment) when they experience disease progression. Details are provided in Section 5.2.2. MSD consultation will be needed prior to starting Second Course Retreatment.

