#### 7.1.8.4.3 Survival Follow-Up

**NOTE: As of Amendment 10, this section is no longer applicable. Subjects currently in survival follow-up are considered to have completed the study; these subjects will no longer be contacted for survival information. Assessment and recording of AEs will be performed as per Section 7.2.**

Subjects who experience disease progression by site assessment or start a new anti-cancer therapy will move into the Survival Follow-Up Phase and should be contacted by telephone approximately every 9 weeks to assess for survival status until death, withdrawal of consent, or the end of the study, whichever occurs first.

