
Sample Size and Power
	
The planned sample size was initially approximately 600 subjects. Japan will begin enrolling late in the enrollment period, and must meet a minimum enrollment regulatory requirement. Therefore enrollment from Japan may continue after enrollment in other countries ends. Total enrollment is now expected to be approximately 700 subjects. For PFS, the trial has ~98% power to demonstrate that pembrolizumab and epacadostat is superior to pembrolizumab and placebo at an overall 1-sided 1.25% alpha-level. For OS, the trial has ~79% power to demonstrate that pembrolizumab and epacadostat is superior to pembrolizumab and placebo at an initial overall 1-sided 1.25% alpha-level. Should the PFS comparison be statistically significant, the 1.25% alpha will be re-assigned to OS. Should the OS comparison be statistically significant, the 2.5% alpha will be re-assigned to ORR. Should the total alpha assigned to OS be 2.5%, the power to demonstrate improved OS with the combination will be about 86%. The treatment effect (true hazard rate) is assumed to be 0.65 for PFS and 0.70 for OS.

Based on review of IA2 data, the DMC recommended that all subjects stop oral therapy (epacadostat/placebo). After study completion, only selected analyses will be performed.

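### In Section 8.11 the expected oral-dose count for subjects who left the study runs to study exit, not to drug stop, so off-drug time can lower percent compliance

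*Combined protocol and SAP*

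**What the plan says.** Section 8.11 gives two rules for the expected number of oral doses. For a subject followed through the whole study period, the count runs from the first treatment day to that subject's final planned dosing day. For a subject who permanently discontinued from the study, it "is the total number of doses from first treatment day to the date the subject discontinued from the study". Percent compliance is doses received over doses expected, times 100, summarised by treatment group in the ITT population.

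Other sections treat the end of treatment and the end of study participation as separate events:

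- Section 5.8.1: "Discontinuation of treatment does not represent withdrawal from the trial".
- Section 5.8.1 also permits an elective stop: "Discontinuation of treatment may be considered for subjects who have attained a confirmed CR and have been treated for at least 8 cycles".
- Section 5.8.2: "A subject must be withdrawn from the trial if the subject or subject's legally acceptable representative withdraws consent from the trial". The only other ground given there is a France-only rule on another malignancy.
- Section 7.1.8.4.2, in force until Amendment 10: "Subjects who discontinue study treatment for a reason other than disease progression will move into the Follow-Up Phase", with imaging every 9 weeks from Week 12 to Week 102.
- Section 7.1.8.4.3, also in force until Amendment 10: telephone contact about every 9 weeks "until death, withdrawal of consent, or the end of the study, whichever occurs first".

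**The concern.** The second rule in 8.11 takes its end date from study exit, and a subject can reach study exit well after the last oral dose. Every day in between adds expected doses that nobody intended the subject to take. A low value for such a subject would then reflect time off drug rather than missed doses.

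The documents foresee subjects who are properly off the oral drug but still in the study. One example is the elective stop after a confirmed complete response. Another is in Section 5.2.1.4 (applicable until Amendment 10), where the oral agent could be stopped for good while pembrolizumab resumed. A third is the stop of all epacadostat and placebo after the second interim analysis, with the study kept open (Sections 2.1 and 8.1). If any of these subjects later withdraws consent, the second rule applies with a gap inside the counting window.

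What is at stake is how an adherence table reads. A trial that found no benefit of the oral agent may be asked whether patients took it, and this rule could make adherence look worse than it was.

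**Working it through.** The plan states no compliance figure, so there is nothing to reproduce. The check applies the 8.11 ratio to a subject who takes every dose until stopping the drug.

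**Inputs**

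- Dosing frequency, used only to count doses: 2 per day. Section 4.2.1.1 says "a dose of 100 mg BID was selected for the Phase 2 portion of Study 202 and for this Phase 3 study".
- Time on drug: 8 cycles of 21 days = 168 days (24 weeks), the earliest elective stop in 5.8.1. Taking this as the stop time is an assumption.
- Time from drug stop to withdrawal of consent: 63 days (one 9-week follow-up interval) or 126 days (two). Both are assumptions.

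**Formula**

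Compliance = 100 × (2 × days on drug) / (2 × days from first dose to the end of the count).

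**Count ended at study exit, as 8.11 is written**

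- Withdrawal 63 days after the stop: received 2 × 168 = 336; expected 2 × (168 + 63) = 462; 336/462 = 72.7%.
- Withdrawal 126 days after the stop: received 336; expected 2 × (168 + 126) = 588; 336/588 = 57.1%.

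**Count ended at drug stop**

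- Both cases: 336/336 = 100%.

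**Sensitivity to the assumed durations**

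The dose frequency cancels, so the result is days on drug / (days on drug + days off drug).

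| Days on drug | 63 days off | 126 days off |
|---|---|---|
| 84 | 84/147 = 57.1% | 84/210 = 40.0% |
| 168 | 168/231 = 72.7% | 168/294 = 57.1% |
| 365 | 365/428 = 85.3% | 365/491 = 74.3% |

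For a fully adherent subject the effect only lowers the score. It grows with off-drug time and is zero when drug and study stop on the same day.

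**The case against.** The best defence is the name of the quantity. Section 8.11 is defining doses that should have been taken on therapy, and after a permitted permanent stop no dose is due. The first rule is also tied to dosing. In addition, the protocol is not strict about these terms. Section 2.1 lists criteria for study withdrawal among the things that end the treatment period, and Section 7.1.7.1 has subjects who leave the trial return for the Safety Follow-Up visit. A sensible programmer might therefore stop at the last dose and obtain 100%.

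Part of this stands: the intent was probably an on-treatment count. But the label is the term being defined, the definition sets a different end date, and no other section overrides it. Two competent programmers could obtain 73% and 100% from the same record.

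The objection that few subjects are affected also stands. Under 5.8.2, withdrawal rests on consent, apart from the France-only rule. Under 7.1.8.4.1, subjects already in follow-up at Amendment 10 count as having completed the study, so they are not in this branch.

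A reader might infer more than the documents support, in three ways:

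- **That deaths make the branch large.** The documents do not say whether death is permanent discontinuation from the study, and 7.1.8.4.3 lists death separately from withdrawal of consent. A subject who dies while on drug has no off-drug time in any case.
- **That the routine 30-day interval after treatment already distorts the score.** Section 7.1.8.4.1 counts a subject who attends the Safety Follow-Up visit as having completed the study, not as having discontinued from it.
- **That the arm summaries or their comparison are biased by a known amount.** Without the number of late consent withdrawals by arm, no such figure can be given.

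**Conclusion.** The point holds as a minor one. As written, the second rule in 8.11 puts off-drug time in the denominator for a subject who stops the oral drug as the protocol allows and later withdraws consent. In the two worked cases full adherence scores 73% and 57% instead of 100%. Those values rest on the assumed 24 weeks on drug and the assumed 9 or 18 weeks to withdrawal.

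The consequence is limited. The summary is descriptive and feeds no test, analysis population or decision rule. Section 8.12 reports treatment duration, and dose intensity as appropriate, separately. Section 8.1 says "After study completion, only selected analyses will be performed" and does not say that compliance is one of them. The efficacy conclusions are untouched.

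**What to change.** In the second rule of 8.11 only, replace the study-discontinuation date with the date of permanent discontinuation of epacadostat/placebo, including the stop after the second interim analysis. If the table is produced, report this as a post-unblinding correction to a descriptive measure.

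The cost is one sentence and the use of oral-drug stop dates. The change touches no dosing or clinical rule. Its downside is that a subject who simply quits the oral drug is scored only up to the stop and can show 100%. The table should therefore be read beside the treatment-duration summary in 8.12.

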### **8.12 Extent of Exposure**

The extent of exposure will be summarized by treatment as duration of treatment in cycles. Dose intensity will also be summarized as appropriate.

## **9.0 LABELING, PACKAGING, STORAGE AND RETURN OF CLINICAL SUPPLIES**

### **9.1 Investigational Product**

The investigator shall take responsibility for and shall take all steps to maintain appropriate records and ensure appropriate supply, storage, handling, distribution and usage of investigational product in accordance with the protocol and any applicable laws and regulations.

Clinical Supplies will be provided by MSD as summarized in [Table 16](#).

Table 16 Product Descriptions

Product Name & Potency	Dosage Form
pembrolizumab 100 mg/4 mL	Solution for Infusion

### **9.2 Packaging and Labeling Information**

Clinical supplies will be affixed with a clinical label in accordance with regulatory requirements.

Pembrolizumab (MK-3475) will be provided as a kitted supply.

### **9.3 Clinical Supplies Disclosure**

**NOTE: As of Amendment 10, blinding is no longer applicable – all subjects will receive open-label pembrolizumab alone.**

This is a blinded trial in which the epacadostat or epacadostat placebo treatment is blinded. However, the pembrolizumab (MK-3475) provided for the trial is open-label; therefore, the subject, the trial site personnel, the Sponsor, MSD and/or designee are not blinded to the

MK-3475 treatment. Treatment (name, strength or potency) is included in the label text; random code/disclosure envelopes or lists are not provided.

The emergency unblinding call center will use the treatment/randomization schedule for the study to unblind subjects and to unmask epacadostat or matching placebo treatment identity. The emergency unblinding call center should only be used in cases of emergency (see Section 7.1.7.2). In the event that the emergency unblinding call center is not available for a given site in this study, the central electronic treatment allocation/randomization system (IVRS/IWRS) should be used in order to unblind subjects and to unmask study treatment identity. MSD will not provide random code/disclosure envelopes or lists with the clinical supplies.

Treatment identification information is to be unmasked ONLY if necessary for the welfare of the subject. Every effort should be made not to unblind the subject unless necessary.

In the event that unblinding has occurred, the circumstances around the unblinding (e.g., date, reason and person performing the unblinding) must be documented promptly, and MSD Clinical Director notified as soon as possible. Only the principal investigator or delegate and the respective subject's code should be unblinded. Trial site personnel, MSD, and Sponsor personnel directly associated with the conduct of the trial should not be unblinded to treatment assignment.

Section 5.8 outlines the criteria for allowing subjects who are discontinued from treatment to continue to be monitored in the trial.

#### **9.4 Storage and Handling Requirements**

Clinical supplies must be stored in a secure, limited-access location under the storage conditions specified on the label.

Receipt and dispensing of trial medication must be recorded by an authorized person at the trial site.

Clinical supplies may not be used for any purpose other than that stated in the protocol.

#### **9.5 Discard/Destruction>Returns and Reconciliation**

The investigator is responsible for keeping accurate records of the clinical supplies received from MSD or designee, the amount dispensed to and returned by the subjects and the amount remaining at the conclusion of the trial. For all trial sites, the local country MSD personnel or designee will provide appropriate documentation that must be completed for drug accountability and return, or local discard and destruction if appropriate. Where local discard and destruction is appropriate, the investigator is responsible for ensuring that a local discard/destruction procedure is documented.

## **9.6 Standard Policies**

Trial site personnel will have access to a central electronic treatment allocation/randomization system (IVRS/IWRS system) to allocate subjects, to assign treatment to subjects and to manage the distribution of clinical supplies. Each person accessing the IVRS system must be assigned an individual unique PIN. They must use only their assigned PIN to access the system, and they must not share their assigned PIN with anyone.

At the close of the trial after unblinding, a letter is to be sent by the investigator to those subjects who received placebos in the image of MSD's product to provide the following advice:

“You have participated in a trial conducted by MSD under the sponsorship of Incyte. This is to advise you that you were among those who received a look-alike tablet created by the Sponsor to resemble the drug epacadostat as much as possible. You did not receive the active drug epacadostat as manufactured by Incyte.”

## **10.0 ADMINISTRATIVE AND REGULATORY DETAILS**

### **10.1 Confidentiality**

#### **10.1.1 Confidentiality of Data**

By signing this protocol, the investigator affirms that information furnished to the investigator will be maintained in confidence, and such information will be divulged to the institutional review board, ethics review committee (IRB/ERC) or similar or expert committee; affiliated institution and employees, only under an appropriate understanding of confidentiality with such board or committee, affiliated institution and employees. Data generated by this trial will be considered confidential by the investigator, except to the extent that it is included in a publication as provided in the Publications section of this protocol.

